5.2 Site Personnel Access to Individual Treatment Assignments

Treatment assignments will be unblinded after database lock. After initial database lock and receipt of written authorization from Amgen to unblind, the unblinded pharmacist or designee will release the specified unblinded pharmacy records to site staff designated to enter the subject treatment into each subject's Unblinded Investigational Product Administration Electronic Case Report Form (eCRF).

A subject's treatment assignment should only be unblinded when knowledge of the treatment is essential for the further management of the subject on this study or may potentially impact the safety of subjects currently enrolled. Unblinding at the study site for any other reason will be considered a protocol deviation. The investigator is strongly encouraged to contact the Clinical Study Manager before unblinding any subject's treatment assignment, but must do so within 1 working day after the event.

6. TREATMENT PROCEDURES

6.1 Classification of Product

The Amgen Investigational Product and/or placebo (except if required by local regulation) used in this study include AMG 334 and matching placebo.

The Non-Amgen Non-investigational product used in this study include: PACAP-38.

The Investigational Product Instruction Manual (IPIM), a document external to this protocol, contains detailed information regarding the storage, preparation, and administration of AMG 334, placebo, and PACAP-38.

6.2 Investigational Product

All investigational products will be administered at the research facility by a qualified staff member. A physician must be present at the time of Investigational Product administration.

6.2.1 Amgen Investigational Product AMG 334

AMG 334 will be manufactured and packaged by Amgen Inc. and distributed using Amgen clinical study drug distribution procedures.

Active AMG 334 will be packaged in open label 5 mL clear glass vials containing 1 mL of 70 mg/mL AMG 334 formulated with mM sodium acetate, $\mathbf{v} \otimes \mathbf{w} \otimes \mathbf{w}$, sucrose, $\mathbf{v} \otimes \mathbf{w} \otimes \mathbf{w}$

All AMG 334 and matching placebo supplies will be shipped to the study site frozen and should be stored at CC °C to CCI C in a non frost-free freezer until ready to use.

For more information regarding investigational product handling and preparation please see the study specific IPIM which is provided as a separate document.

6.2.1.1 Dosage, Administration, and Schedule for AMG 334

Single doses of AMG 334 up to 210 mg SC or 140 mg IV were found to be generally well tolerated in both healthy subjects and migraine subjects (FIH Study 20101267). While the AMG 334 exposure and its migraine prevention efficacy relationship is to be established, a high dose of AMG 334 (140 mg intravenous, IV) is selected for this study in order to provide maximum CGRP receptor blockade against the PACAP-38 challenge.

After a single IV administration of AMG 334 at 140 mg, the distribution phase of serum AMG 334 was approximately completed by Day 8 (20101267, Figure 1). The mean serum AMG 334 concentration on Day 8 was 15.4 μ g/mL, which is similar to the C_{avg} (15.9 ug/mL) of AMG 334 after the third 140 mg SC monthly dose administration. Monthly SC 140 mg administration is one of the higher dose regimens currently being evaluated in Phase 2 migraine clinical trials. Based on this information, Day 8 is considered as an appropriate time point to provide similar target coverage as in AMG 334 Phase 2 migraine clinical trials coverage and thus is selected for PACAP-38 challenge.

IV route is being chosen over subcutaneous (SC) as it is the faster route to achieve the target concentration after AMG 334 administration.

Figure 1. Mean (+SD) Serum AMG 334 Concentration-time Profiles After Intravenous Administration of AMG 334 at 140 mg

A single dose of 140 mg of AMG 334 or matching placebo will be administered intravenously on Day 1. The quantity, volume, start date/time, stop date/time, and blinded investigational product concentration will be recorded on the individual subject's Blinded Investigator Product Administration eCRF prior to initial database lock. Following initial database lock, upon written authorization from Amgen, the package lot number and unblinded dose of the investigational product will be recorded on each subject's Investigational Product Administration eCRF.

Time (day)

The effects of overdose of AMG 334 are not known. Overdose with this product has not been reported. All overdose occurrences must be documented and corresponding adverse events must be recorded on the appropriate eCRF and in the source documents.

The dosing schedule is described by a schema in the protocol synopsis.

6.2.1.2 Dosage Adjustments, Delays, Rules for Withholding or Restarting, Permanent Discontinuation for AMG 334

Further dosing of AMG 334 will be stopped or modified to a lower dose if suspected adverse drug reactions and/or changes in safety data (including but not limited to vital signs, ECG, or clinical laboratory results) are observed and these changes pose a health risk.

Clinically or medically significant suspected adverse drug reactions, and serious adverse events considered to be related to study procedures will be followed until resolved or considered stable. The study may be terminated at any point in time at the discretion of the sponsor.

The dosing schedule is described by a schema in the protocol synopsis.

6.3 Non-Amgen Non-Investigational Product

6.3.1 Non-Amgen Non-Investigational Product PACAP-38

Non Amgen non-investigational product PACAP-38 will also be used in this study.

All non-Amgen non-investigational products will be administered at the research facility by a qualified staff member. A study physician must be present at the time of product administration.

Additional details regarding the products are provided in the IPIM.

6.3.1.2 Dose-cohort Study Escalation and Stopping Rules for PACAP-38

In order to ensure subject safety and select the lowest PACAP-38 dose that will ideally trigger headache in all subjects within a given cohort and moderate to severe MLAs in

the majority of the subjects within the same cohort, a dose selection strategy, along with Safety Review Meetings and Dose-Level Review Meetings (DLRM) have been implemented. Dosing of PACAP-38 shall not exceed a total dose of 115 pmol/kg, providing an approximate 10X exposure margin over the non-clinical NOAEL dose. However, the trigger of headaches in the majority of the subjects within a given cohort and mild, moderate or severe MLAs in the majority of the subjects within the same cohort may be considered acceptable to advance to the randomized portion of the study (Part B).

Up to five cohorts consisting of approximately 2 to 5 subjects are planned. Based on emerging safety and tolerability data, as well as the number of subjects experiencing a headache and/or MLA, the voting members of the Safety Review Meetings or DLRM (the PI, Medical Monitor and Global Safety Officer), may decide cohorts should be removed or additional cohorts should be added, with a maximum of 5 total cohorts. Subject numbers within each cohort may also be increased or decreased based on the decision from the Safety Review Meeting or DLRM. Doses to be administered within each cohort may be repeated, higher or lower than the last dosed cohort. Dosing of any subject shall not exceed 115 pmol/kg. Possible future PACAP-38 doses and associated cohorts beyond 100 pmol/kg (Cohort 4) are as follows: 115 pmol/kg (Cohort 5).

On Day 1, approximately 2 subjects in Cohort 1 will receive an infusion of 10 pmol/kg/min over 2.5 minutes (total dose 25 pmol/kg). The PI will be responsible to review heart rate (HR) and blood pressure (BP). The BP assessment is based on a single measurement of systolic blood pressure (SBP) of >150 mm Hg or diastolic blood pressure (DBP) > 100 mm Hg. If the mean heart rate increase of the subjects in Cohort 1 is greater than 50% over baseline during a 2 hour period after dosing and SBP does not increase to >150 mm Hg or DBP to >100 mm Hg, then approximately 3 subjects in Cohort 2 will receive an infusion of 10 pmol/kg/min over 5 minutes (total dose 50 pmol/kg). Written documentation from Amgen of the decision to proceed with enrollment in Cohort 2 is required. After dosing Cohort 2 and any subsequent cohort, the PI will again be responsible to review HR and BP using previously outlined criteria. These same criteria shall also be assessed for Cohort 3.

After dosing Cohort 3, up to 5 subjects in Cohort 4 will receive 10 pmol/kg/min over 10 minutes (total dose 100 pmol/kg). Following Cohort 4, a Dose-Level-Review Meeting (DLRM) will occur to decide the dose of PACAP-38 to be used in the randomized portion of the study (Part B). This decision will be primarily based on safety and tolerability data,

and number of subjects experiencing a headache and/or MLA in Cohort 4, although all of the available data for Cohorts 1 to 4 will be reviewed. The dose- selection for Part B will be based on the goal of ensuring subject safety and ideally triggering headache in all subjects within a given cohort and moderate to severe MLAs in the majority of subjects within the same cohort. However, the trigger of headaches in the majority of subjects within a given cohort and mild, moderate or severe MLAs in the majority of subjects within the same cohort may be considered acceptable to advance to the randomized portion of the study (Part B). If this goal is not achieved, following the DLRM review of the Cohort 4 data, then Cohort 5 dosing of 10pmol/kg/ min over 11.5 minutes (total dose 115 pmol/kg) can commence.

Cohorts 2, 3 and 4 enrollment will occur after a Safety Review Meeting between the principal investigator (PI), medical monitor (MM), and global safety officer (GSO) or designee. At that time, available vital signs and adverse events occurring at least 24 hours following PACAP-38 dosing will be reviewed.

If the PI, MM, and GSO or designee decide not to proceed with enrollment into a subsequent cohort, then a Safety Review Meeting or DLRM will be held after the last dosed cohort. Refer to Section 10.4.2 for additional information on the Safety Review Meetings and DLRMs. The Safety Review Meeting or DLRM voting members will decide whether or not to proceed with enrollment in Part B Randomization (AMG 334 or Placebo) Phase and if the decision is made to proceed, the Safety Review or DLRM voting members will select the appropriate PACAP-38 dose. The decision to proceed with Part B of the study will be based on the goal of ensuring subject safety and ideally triggering headache in all subjects within a given cohort and moderate to severe MLAs in the majority of subjects within a given cohort and mild, moderate or severe MLAs in the majority of subjects within the same cohort may be considered acceptable to advance to Part B of the study.

All available study data, including the headache questionnaires, demographics, investigational product administration, medical history, concomitant medications, adverse events (including MLA), ECGs, vital signs, and laboratory results will be reviewed. Data to be reviewed at the DLRMs during the PACAP-38 Dose Selection Phase will not be blinded. Data to be reviewed for any unscheduled DLRM post the PACAP-38 Dose Selection Phase will be reviewed blinded (ie, treatment assignment will not be revealed) unless unblinding is deemed necessary for the review team to make

dosing decisions. If deemed necessary, unblinding will be performed to assist dose decisions in accordance with Amgen standard procedures.

6.3.1.3 PACAP-38 - Dosage Adjustments, Delays, Rules for Withholding, or Restarting Stopping or Permanent Discontinuation

Dosing of PACAP-38 will be stopped or modified by the DLRM voting members if suspected unexpected treatment related adverse events of Grade 2 or greater in the same system organ class occur in 2 or more subjects or Grade 3 occur in 1 or more subject. Dosing of PACAP-38 will also be stopped or modified by the DLRM voting members under the following circumstances:

- a) Blood pressure:
 - a. Systolic BP > 150 mm Hg OR
 - b. Diastolic BP > 100 mm Hg OR
 - c. Decrease in SBP from baseline > 30 mm Hg OR
 - Decrease in DBP from baseline > 15 mm Hg and considered clinically relevant after consultation between the investigator and the medical monitor.

Any changes in blood pressure as defined above must be confirmed with 3 consecutive measurements taken approximately 5 minutes apart and with the subject remaining in a semi-recumbent position. The mean of the 3 measurements will be the final recorded value.

- b) Mean heart rate increase of subjects in a given cohort is greater than 50% or greater than 20% decrease over baseline during a 2 hour period after dosing
- c) Changes in other vital signs or clinical laboratory results considered to pose a significant health risk to subjects

In addition, any clinically or medically significant suspected adverse drug reactions and serious adverse events considered to be related to study procedures will be followed until resolved or considered stable.

The study may be terminated at any point in time at the discretion of the sponsor.

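### The heart-rate condition for dosing the next PACAP-38 cohort is the same event that triggers the stopping rule; a "not" appears to be missing

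*Protocol*

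**What the plan says.** Protocol 6.3.1.2 opens the escalation condition with "If the mean heart rate increase of the subjects in Cohort 1 is greater than 50% over baseline during a 2 hour period after dosing". It completes the condition with a blood-pressure limit, followed by the action: "SBP does not increase to >150 mm Hg or DBP to >100 mm Hg, then approximately 3 subjects in Cohort 2 will receive". The criteria are then carried forward: "After dosing Cohort 2 and any subsequent cohort, the PI will again be responsible to review HR and BP using previously outlined criteria". The same sentence stands in the protocol synopsis, in Protocol 3.1 and, with heart rate abbreviated, in the design summary of SAP 3.1.

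Section 6.3.1.3 introduces its list with "Dosing of PACAP-38 will also be stopped or modified by the DLRM voting members under the following circumstances". Item b) of that list reads "Mean heart rate increase of subjects in a given cohort is greater than 50% or greater than 20% decrease over baseline", over the same 2-hour window. Item a) holds the blood-pressure limits: the 150/100 mm Hg ceilings, a fall in systolic pressure of more than 30 mm Hg, and "Decrease in DBP from baseline > 15 mm Hg and considered clinically relevant after consultation between the investigator and the medical monitor".

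On process, "Cohorts 2, 3 and 4 enrollment will occur after a Safety Review Meeting". If the headache and migraine goals are not reached at Cohort 4, "then Cohort 5 dosing of 10pmol/kg/ min over 11.5 minutes (total dose 115 pmol/kg) can commence" after the dose-level review.

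**The concern.** The two rules use the same quantity (cohort mean heart-rate rise over baseline), the same threshold (more than 50%) and the same window (2 hours), and they prescribe conflicting actions. Neither document says which prevails. PACAP-38 is expected to raise heart rate, so a rise above 50% is a foreseeable result. In that case one sentence tells the investigator that the condition for a higher dose is met, and the next section tells the voting members to stop or modify dosing. The carried-over duty to review later cohorts points back to the sentence that runs the wrong way.

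**Working it through.** The plan gives no figure to reproduce, so the check compares the two rules as sets of results.

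**The overlap.**
- Proceed, as written: rise >50% and pressure not above 150/100.
- Stop or modify, item b): rise >50%, or fall >20%.

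The first set lies inside the second, so every result that meets the written proceed condition also meets item b).

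**All combinations.** Cross heart-rate change (fall >20%; between −20% and +50%; rise >50%) with pressure above 150/100 (yes/no), a pressure-decrease limit met (yes/no) and any other 6.3.1.3 criterion met (yes/no): 3 × 2 × 2 × 2 = 24 combinations.

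| Proceed condition | Combinations that proceed | Of these, also meet a stopping criterion |
|---|---|---|
| As written | 1 × 1 × 2 × 2 = 4 | 4 |
| With *not* only | 2 × 1 × 2 × 2 = 8 | 7 |
| With *not* and no other 6.3.1.3 criterion met | 1 | 0 |

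One combination is free of every stopping criterion: heart rate between −20% and +50% with nothing else met. The written condition is not satisfied there. The counts show logical coverage and are not probabilities.

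**Numerical grid.** Heart-rate change from −40% to +120% in steps of 1, systolic pressure 80 to 180 and diastolic 50 to 120 in steps of 5, give 161 × 21 × 15 = 50,715 cells.
- As written, 70 × 15 × 11 = 11,550 cells allow escalation, and all 11,550 meet item b).
- Of the 71 × 15 × 11 = 11,715 cells that meet neither item b) nor the upper pressure limits, none allows escalation.
- With *not* alone, 91 × 15 × 11 = 15,015 cells allow escalation. Of these, 20 × 15 × 11 = 3,300 still meet the >20% fall in item b), so *not* alone is insufficient.

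**Heart-rate scale.** Exclusion 4.2.11 caps baseline at 85 beats/min. If a whole cohort averaged that ceiling, the literal text would require a mean above 1.5 × 85 = 127.5 beats/min before the next cohort is dosed. At assumed baseline means of 60 and 70 it would require more than 90 and 105.

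**Remaining reach.** Subjects dosed so far: 2 + 3 + 2 (Protocol 2.4) + 4 (Amendment 3 summary) = 11, in four cohorts. The planned upward step left is Cohort 5: at most 5 of the 25 Part A subjects (20%), with a dose increase of 115/100 − 1 = 15%. The NOAEL margin in Table 1 falls from 11.4x to 10.0x. Expansions at doses already given are not counted.

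**Evidence for a missing *not*.** The blood-pressure half of the sentence is written as a safety ceiling, and item b) uses 50% as a limit. The Amendment 2 and 3 summaries report ascending cohorts with no subject meeting stopping criteria. That last point is indirect, because item b) is a cohort mean and the reports are about subjects.

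**The case against.** The strongest reply is that the sentence has done no harm and has little left to do. Its one explicit action, Cohort 1 to Cohort 2, is finished. If the reports of no stopping criteria met extend to the cohort mean, the literal condition was never satisfied and escalation went ahead anyway, so the team read it correctly. Protocol 2.4 schedules a Safety Review Meeting or DLRM before any dose increase, and the voting members at those meetings are the people who apply 6.3.1.3. Cohort 5 is gated by the DLRM and the headache and migraine goal, and the carried-over text is a duty to review, not a trigger. The Amendment 3 rationale expects the 115 pmol/kg step not to be taken. Section 6.3.1.2 also lets the voting members repeat, raise or lower the dose, so the sentence is an *if* and not an *only if*. Item b) permits modification as well as stopping.

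All of this stands and limits the practical risk. None of it reconciles the two rules.

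Two further points also stand. Escalation judges pressure on a single reading, whereas 6.3.1.3 requires three confirmatory readings; the 24-combination count merges them. If they are split, an unconfirmed high reading meets neither *proceed* nor *stop*, but the overlap on heart rate is unchanged. In addition, the SAP cites Protocol Amendment 4, while the protocol supplied is Amendment 3, so the later protocol text cannot be checked. The SAP of 17 May 2017 still carries the sentence.

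**Conclusion.** The concern holds and should be fixed. As written, the condition to proceed is wholly contained in a stopping rule (4 of 4 combinations), and the one fully stop-free combination does not satisfy it. That conclusion rests on the text alone. The missing *not* is an inference; if a rise above 50% was really meant as a sign of activity, item b) would have to change instead. The remaining reach is 0 to 5 subjects in Cohort 5, and 0 is plausible. If Part A has closed, the correction only clarifies the record. The efficacy comparison and its operating characteristics are untouched.

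**What to change.** Have the clinical team confirm the intended direction. Then reword the condition so that Cohort 2 is dosed if the Cohort 1 mean heart-rate rise is *not* greater than 50% over baseline in the 2 hours after dosing, pressure does not exceed 150/100 mm Hg, **and no other Section 6.3.1.3 criterion is met**. The added clause brings in the >20% heart-rate fall and the pressure-decrease limits, so no result can meet both rules, and the criteria carried to later cohorts then point the right way. It would also help to say how an unconfirmed single high pressure reading is handled; under this wording it does not satisfy the condition to proceed.

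Make the change in the synopsis, Protocol 3.1, Protocol 6.3.1.2 and SAP 3.1. The cost is one word and one clause in four places, with no added subjects, procedures or analyses.

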7.2.7 Adverse Event

Adverse event and serious adverse event assessments will be made throughout the study and will be evaluated and recorded in the source documents and on the eCRF for the duration of the study. Determination of the severity of all adverse events will be consistent with CTCAE Version 4.0 unless specified otherwise.

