9.1.3 Serious Adverse Events

A serious adverse event is defined as an adverse event that meets at least 1 of the following serious criteria (unless it meets the definition of a Disease-Related Event as defined in Section 9.1.1):

- fatal
- life threatening (places the subject at immediate risk of death)
- requires in patient hospitalization or prolongation of existing hospitalization
- results in persistent or significant disability/incapacity
- congenital anomaly/birth defect
- other medically important serious event

A Disease-Related event is to be reported as a serious adverse event if,

- the subject's pre-existing condition becomes worse than what the investigator would consider typical for a patient with the same underlying condition, or
- if the investigator believes a causal relationship exists between the investigational medicinal product(s)/protocol-required therapies and the event,
- and the event meets at least 1 of the serious criteria above.

An adverse event would meet the criterion of "requires hospitalization", if the event necessitated an admission to a health care facility (eg, overnight stay).

If an investigator considers an event to be clinically important, but it does not meet any of the serious criteria, the event could be classified as a serious adverse event under the criterion of "other medically important serious event". Examples of such events could include allergic bronchospasm, convulsions, blood dyscrasias, drug induced liver injury (DILI) (see Appendix A for DILI reporting criteria), or events that necessitate an emergency room visit, outpatient surgery, or urgent intervention.

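### Read literally, the PACAP-38 adverse-event criterion in Protocol 6.3.1.3 is met by one Grade 3 event but not by one Grade 4 or 5 event; its two limbs need to be reconciled

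*Protocol*

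**What the plan says.** Protocol 6.3.1.3 opens with the consequence: "Dosing of PACAP-38 will be stopped or modified by the DLRM voting members if" one of two conditions on graded adverse events holds. The thresholds in that sentence read: "Grade 2 or greater in the same system organ class occur in 2 or more subjects or Grade 3 occur in 1 or more". Taken apart, they give two limbs.

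- Two-subject limb: "suspected unexpected treatment related adverse events of Grade 2 or greater in the same system organ class occur in 2 or more subjects".
- Single-subject limb: "Grade 3 occur in 1 or more subject".

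The section then adds non-graded triggers. Item a covers blood pressure and item b the mean heart rate of a cohort. Item c reads "Changes in other vital signs or clinical laboratory results considered to pose a significant health risk to subjects". The section closes with a general reservation: "The study may be terminated at any point in time at the discretion of the sponsor".

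The scale is fixed in Protocol 7.2.7: "Determination of the severity of all adverse events will be consistent with CTCAE Version 4.0 unless specified otherwise". The protocol does not print the grade definitions. It does foresee events at the top of the severity range, since the serious criteria in 9.1.3 include fatal events and those that are "life threatening (places the subject at immediate risk of death").

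**The concern.** The two limbs sit in one sentence and treat the upper end of the scale differently. The first is explicitly open above Grade 2; the second names a single grade. A severity criterion should not stop being met as the event gets worse, and this one does if followed to the letter.

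It matters because this is the only criterion in 6.3.1.3 expressed in adverse-event grades, and neither limb is confined to Part A. Part A exposes up to 25 subjects to PACAP-38 and Part B up to 36 (Protocol 10.2). Protocol 10.4.2 plans a DLRM for the dose-selection subjects only. In Part B, then, no scheduled DLRM stands behind the written trigger, although unscheduled ones can be called.

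**Working it through.** The plan states no figure for this rule, so there is none to reproduce. The check applies the sentence literally to each grade.

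**Inputs**
- Two-subject limb, L1 (6.3.1.3): true if, within some system organ class (SOC), at least 2 subjects have an event of Grade ≥ 2.
- Single-subject limb, L2 (6.3.1.3): true if at least 1 subject has an event of Grade = 3.
- Criterion met if L1 or L2 is true.
- Scale: CTCAE 4.0 (7.2.7 and Appendix A), taken to run from Grade 1 to Grade 5.
- All events are assumed to be suspected, unexpected and treatment related, and not accompanied by a change that meets items a to c.

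**Result, literal reading**

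| Grade | One subject | Two subjects, different SOCs | Two subjects, same SOC |
|---|---|---|---|
| 1 | not met | not met | not met |
| 2 | not met | not met | met (L1) |
| 3 | met (L2) | met (L2) | met (L1 and L2) |
| 4 | **not met** | **not met** | met (L1) |
| 5 | **not met** | **not met** | met (L1) |

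In the first two columns the criterion switches on at Grade 3 and off again at Grade 4. It is not monotone in severity for a single event, nor for two events in different SOCs. For two subjects in the same SOC there is no gap. A Grade 4 or 5 event also counts towards L1, so a later event of Grade 2 or greater in another subject in that SOC would complete it.

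**If L2 is read as including higher grades**, the four bold cells become met and the ordering is restored. This comparison only locates the inconsistency; it does not say which reading is intended.

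**Does other text close the gap?**
- Items a to c of 6.3.1.3 name blood pressure, heart rate, other vital signs and laboratory results. A Grade 4 or 5 event meets them only if it comes with such changes.
- The Amendment 2 summary of modified stopping rules lists those same items and no adverse-event grade.
- The SAP does not restate the adverse-event criterion.
- Protocol 2.2.2.1.3 and 2.2.2.2.3 write the grade with a ≥ sign when Grade 3 and above is meant, so the protocol does use both forms.

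**The case against.** **The literal reading is selective.** The single-subject limb is elliptical. It has no noun and takes its qualifiers (suspected, unexpected, related) from the first limb. A reader who carries those over could carry the open upper end over too, and then there is no gap. Nothing suggests that the sponsor meant to exempt Grade 4 or 5. This stands in part: a drafting omission is the likely explanation, and a sensible team would probably read the limb as open. It does not remove the point. The same sentence writes the open end for Grade 2 and omits it for Grade 3, and a safety criterion should not depend on how an ellipsis is resolved.

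**The event would not go unseen.** This stands. Serious adverse events go to the sponsor within 24 hours (9.2.2.2). The safety officer, medical monitor and principal investigator review adverse events throughout (9.2.2.4). A Safety Review Meeting or DLRM follows each Part A cohort, and any voting member can call an unscheduled DLRM (10.4.2). A reader might infer that the sponsor's right to terminate is the only fallback; these provisions show otherwise. They are, however, reporting or discretionary steps. None of them obliges the voters to stop or modify dosing.

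**The consequence is not an automatic halt.** This also stands. A reader might take the rule as a hard stop that a Grade 4 event escapes. Meeting it means that the voting members stop or modify dosing, and the form of action is theirs to choose.

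**The text may be superseded.** The protocol supplied is dated 01 September 2016 (Amendment 3). SAP section 1 cites Amendment 4, dated 21 October 2016, which was not supplied. Whether 6.3.1.3 still reads this way is unknown.

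**Conclusion.** The point holds as an internal inconsistency in a stated safety criterion. Followed literally, one suspected, unexpected, related Grade 3 event obliges the voting members to stop or modify PACAP-38 dosing. One Grade 4 or 5 event, or two in different SOCs, does not, unless items a to c are also met. What is lost is the pre-specified obligation to act, not the review of the event or the authority to act on it.

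No probability is attached. A reader might try to calculate how often the two-subject limb would stay unmet within one small cohort after a single Grade 4 event. The documents do not support that: they give no rate for qualifying events, and the two-subject limb has no cohort restriction, unlike the heart-rate item, which is expressly tied to a given cohort. The Amendment 3 rationale reports no serious adverse events and no subject meeting the stopping criteria in the four cohorts dosed by then, so nothing documented shows that the gap has mattered in practice.

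The conclusion rests on the wording of the supplied protocol and on CTCAE 4.0 extending to Grades 4 and 5.

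**What to change.** The sponsor's safety team should reconcile the two limbs of the graded criterion in Protocol 6.3.1.3 and state explicitly how the single-subject limb treats events graded above the one it names. They should first check whether the wording persists in Amendment 4. Which grades trigger action, and what action follows, are for that team to decide; no threshold is proposed here. The cost is a few words in one section, with no extra data, visits or subjects and no effect on the statistical analysis.
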